3.1.1 Assessment subset 1: Identification data

This section includes:

- the participant's ID number: a four digit number where the first number corresponds to the center (1 for Patras, 2 for Nicosia and 3 for Nancy) and the three following to the number given to each participant when they enter the study. This ID number is unique, and serves to identify and spot a participant all throughout the study.
- the group allocation: according to the order of entering the study and the ID numbers, individuals are allocated in groups START UP, MAIN, EVALUATION and CONTROL, as described in section 2.3.
- the date of entry in the study: corresponds to the date of informed consent signature
- the subject's initials: to avoid personal identity unmasking in the e-CRF only the first two letters of the participants' first and last name are noted.
- year of birth: since only rough chronological age serves equally well the purposes of the study, no exact date are noted in order to avoid the risk of personal identity unmasking.
- sex

The identification data, since they remain unchanged in time, are collected only once during the first clinical evaluation appointment and from that point on only the ID number will be used to identify each subject. Each center holds the responsibility to keep separate and secured archives of more extended identification data of each participant, including their contact details. Table 4, summarizes this sub questionnaire.

Table 4. IDENTIFICATION DATA

Participant ID number	
Group	START/ MAIN / EVALUATION/ CONTROL
Date of entry in the study	Corresponds to the date of the consent signature
Name initials	First two letters of First and Last name
Year of birth	
Sex	M/F

3.1.2 Assessment subset 2: Generalities and demographics

This section serves for the collection of some demographic data and also as a means to establish the first contact with the participant and smoothly introduce the whole battery. It includes:

- information about the living conditions: mostly to investigate the level of isolation and the need of external help
- family status
- profession: as an indirect index of socio-economic status
- education: as an indirect index of socio-economic status and helpful co-variable to interpret some tests
- leisure activities and
- social life/communication: as indices of social activity, social surroundings and modern means of communication usage.

Obviously, the items referring to education and profession are filled in only once during the first clinical evaluation appointment. The rest of the information will be collected repeatedly. Table 5 summarizes this sub questionnaire.

Table 5. GENERALITIES AND DEMOGRAPHICS

Living	Choose all that apply:
conditions	1.lives alone
	2.live with spouse/companion
	3.live with another/other relative(s)
	4.family/close friends nearby
	5.Presence of regular help (professional or family)
Family status	Choose one answer:
	1.Single
	2.Married or in a relationship
	3.Divorced
	4.Widow
Profession	Chaosa ang angwar
Profession	Choose one answer:
	1-Housewife
	2-Agriculture Workers (farmer, breeder etc)
	3-Workers (manual labor workers, factory workers)
	4-Craftsmens, Merchants (enterprising, businessmen etc)
	5-Intermediary professions (ex. sailors? seamen? drivers? Free professionals?)
	6-Employees, Officers, Clerks
	7-Executive employees and intellectual professions (teachers, professors, tutors, physicians, engineers, lawyers etc)
Education	Number of educational years
	Write down the number. Values of 0 also acceptable
Leisure	How many times do you go out of your house per week?
activities	Write down the number. Values of 0 or decimals also acceptable. "I don't know" option also provided
	Are you member to a club or an association? Yes/No
1	

How many times per week do you exchange visits with somebody (either Social life/ communication you visit them or vice versa)? Write down the number. Values with decimals also acceptable. "I don't know" option also provided How many times per week do you receive or give telephone calls (or other means of distance communication) with someone close? Write down the number. Values with decimals also acceptable. "I don't know" option also provided What is the mean time you spend speaking at the phone per week (in minutes)? Write down the number. Values with decimals also acceptable. "I don't know" option also provided What is the mean time you spend on videoconference per week (in minutes) either on your own of assisted by someone else? Write down the number. Values with decimals also acceptable. "I don't know" option also provided What is the mean number of text messages you send per week either on your own or assisted by someone else? Write down the number. Values with decimals also acceptable. "I don't know" option also provided

3.1.3 Assessment subset 3: Medical history, comorbidities, medication list

This session compiles the medical history of the patient, mostly as it is reported by him or herself and extracted from the available medical records. Of course, this system bears some risks as far as the validity of the available data is concerned, but it is a methodology widely employed in large studies which do not aim primarily in the detailed study of each and every one of the corresponding co-morbidities. The focus of the present study is frailty and therefore there is no need in a thorough analysis with all diagnostic means for other pathologies.

In case of a serious medical condition such as an active psychiatric disorder, an advanced malignancy or other terminal illness of an estimated life expectancy of less than 12 months

or substance abuse comes out from the history taking, the subject are excluded from the study. The data to be collected, as well as its rational, consist of:

- Identification of an existing pathology from a pre-given list of common medical conditions with importance to older adults, based on self-reporting and available medical records' review (annex 1).
- Estimation by the physician of the effect of each of the comorbidities in the individual's functional status. This information provides us with an insight of the importance of each comorbidity and therefore its contribution to frailty. By this way the list of comorbidities obtains more than a catalogue value and reveals a short of ranking of their importance for frailty (annex 1).
- Lead comorbidity identification, according to the three comorbidities that were determined as important by the study's initial protocol: prior stroke history, mild cognitive impairment and osteoarthritis for men and osteoporosis for women (annex 2).
- Medication list: active substances and daily administration frequency will be recorded. Centralization of this information will allow to further prescription analysis and categorization of drugs takes according to the British National Formulary model. Polymedication is considered a major factor and index of frailty (3), while the frequency of daily drug taken is an index of burden in the everyday life of an individual and at the same time a potential source of medication errors (annex 3).
- Hospitalizations: which are considered an outcome unfavorable for older adults as they threaten autonomy (4) and in the same time frailty affects the outcomes of a hospitalization (5).
- Falls history: major geriatric syndrome closely related to frailty (6)
- Fractures history, date and localization. Fractures are a major complication of falls and negatively affect functional status.
- Physical activity is considered a major preventive measure against frailty, and at the same time its restriction constitutes criterion of frailty (7), (8), (2).
- Smoking status and
- Alcohol use: is of interest as habits significantly affecting health status. Moreover, the notion of excessive alcohol use is an exclusion criterion for the study. Alcohol use is quantified according to recommended use of no more than 3-4 alcohol units for men (3 for our study) and no more than 2-3 units for women (2 for our study). The alcohol units' equivalences that are going to be consulted are illustrated in annex 4 (9).

Table 6 summarizes this sub questionnaire.

Table 6. MEDICAL HISTORY, COMMORBIDITIES, MEDICATION LIST

Medical conditions	and	Surgical	Comorbidities as self-reported by the participants and/or revealed
conditions			by their medication list and/or medical records. (Annex 1)
			Check all that apply
			 ARTERIAL HYPERTENSION yes/no DYSLIPIDEMIA yes/no DIABETES MELLITUS yes/no ISCHEMIC HEART DISEASE yes/no CHRONIC ATRIAL FIBRILLATION/PAROXYSMAL AF OR OTHER ARRYTHMIA yes/no HEART INSUFFICIENCY yes/no STROKE OR TIA yes/no CHRONIC RENAL DISEASE yes/no CANCER yes/no RESPIRATORY DISEASE yes/no IMPAIRED COGNITIVE FUNCTION yes/no PARKINSON'S DISEASE yes/no EPILEPSY yes/no DEPRESSIVE MOOD yes/no ANXIETY AND/OR SLEEP PROBLEM yes/no URINARY INCONTINENCE yes/no PROSTATE PATHOLOGY yes/no ANEMIA yes/no JOINT PAIN- MUSCULOSCELETAL COMPLAINTS/DISEASES yes/no OSTEOPOROSIS yes/no CONSTIPATION AND OTHER INTESTINAL PATHOLOGY yes/no THYROID GLAND PATHOLOGY yes/no EYE DISEASES yes/no HEARING PROBLEMS yes/no HEARING PROBLEMS yes/no HEARING PROBLEMS yes/no CONSTIPATION AND OTHER INTESTINAL PATHOLOGY yes/no DISPESS Yes/no DISEASES yes/no DUSPEPSY yes/no THYROID GLAND PATHOLOGY yes/no EYE DISEASES yes/no HEARING PROBLEMS yes/no HEARING PROBLEMS yes/no EVE DISEASES yes/no HEARING PROBLEMS yes/no HEARING PROBLEMS yes/no HEARING PROBLEMS yes/no
			SIGNES yes/noOthers (ICD-10 coding) yes/no
F		((
Estimation			,
each como individual's	-	in the	impact in the individual's functional capacity? yes/no

Lead co-morbidity among those with special interest for the study	 Which is the most important lead co-morbidity (Annex 2): One answer possible Prior stroke MCI Osteoporosis if woman /Osteoarthritis if man None of the above No comorbidity at all
Medication	The whole medication list (Annex 3) (drugs over-the-counter and drug frequently- even not daily- used included)
	Frequency of drug administration per day
	How many times a day (s)he takes each distinct drug
Hospitalization	Number of hospitalizations in the last year
	"I don't know" option also provided
	Number of-hospitalizations in the last year and three years?
	"I don't know" option also provided
Falls	Number of falls in the last year
	"I don't know" option also provided
Fractures	Number of fractures during the last 3 years
	"I don't know" option also provided
	Number of fractures in lifetime
	"I don't know" option also provided

[figure not shown]
	Fractures' anatomic localization.	
	Click all that apply:	
	 upper limps hip-pelvis vertebral other multiple factures "I don't know" option also provided	
	How many months before the study did your last fracture occur? "I don't know" option also provided	
Physical Activity	Do you have regular physical activities (walking gardening, others). One choice	
	 -No -<2h per week -2-5 h per week ->5 h per week 	
Smoking status	 Never smoked Past smoker (stopped at least 6 months) Current smoker 	
Alcohol use	Number of alcohol units' equivalences consumption per week (Annex4).	
	Values of zero or decimals also accepted	

[figure not shown]
3.1.4 Assessment subset 4: Clinical examination and instrumental measurements

This session will include mostly the instrumental part of the clinical evaluation.

 Arrhythmia detection by pulse palpation by a physician. The interest for this is that some automated measurements such as the blood pressure taken by an electronic tensionmeter and the measurements of the mobilograph can be influenced by the presence of an arrhythmia.

- Height measurement: in order to calculate BMI
- Weight measurement: weight lost over time is an important element of frailty. Obesity, on the other hand, can bear other health risks, mostly cardiovascular disease related. An electronic scale is employed.
- BMI: is calculated by the values of height and weight and will serve as a more complete assessment of body mass. Furthermore, it is necessary for the MNA questionnaire which assesses nutritional status.
- Impedance/body fat. A special electronic scale is employed. In order to do this measurement, shoes and socks have to be removed.
- Waist circumference. This measurement will serve as an index of abdominal obesity, closely related to metabolic syndrome. The measurement of waist circumference is done in the standardised way illustrated in figure 2.

Measurement should be done at the end of the expiration

Figure 5. Waist circumference measurement methodology

- Chest circumference. This measurement serves in order to specify the right size for the WWBS device.
- Blood pressure measurements. After the subject has rested in sitting resting position during at least 10 minutes, three consecutive measurements are taken, one minute apart from one another, with an electronic tensionmeter. A mean value of the second and third measurement is automatically calculated (first measurement rejected as "trial" measurement). Simultaneously, the heart rate (HR) is measured as well.
- Orthostatic hypotension detection. After passing in standing position, two BP and HR measurements take place, one in the first and the other in the third minute after getting up. Each of these standing measurements is compared with the mean of the sitting ones. The presence of orthostatic hypotension is confirmed if the difference in systolic BP is ≥20mmHg and/or the difference in diastolic BP is ≥10mmHg. Heart rate is also evaluated in a secondary analysis to see if there is a tendency of compensation by HR augmentation. The research for orthostatic hypotension is crucial when evaluating the autonomic system function and the fall risk. The presence of the

investigator near the participant eliminates the risk of falling during the test. Measurement are done with an electronic tensionmeter.

• Arterial stiffness evaluation. These measurements are performed by the mobil-Ograph. This non interventional method bears no risks for the individual.

Table 7 summarises this sub questionnaire.

Arrhythmia detection	Pulse palpation. Is the pulse regular or not?
	1. Yes=absence of arrhythmia
	2. No= presence of arrhythmia
Height measurement	In meters
Weight measurement	In kilograms
ВМІ	Automatically calculated by the formula: BMI=weight(in kgs)/height(in meters) ²
Impedance -Body fat	Measurement by FORA device
Waist circumference	In centimeters
Chest circumference	In centimeters
Blood pressure measurements	3 measurements (one minute apart) in sitting position
	(Mean calculation of 2 nd and 3 rd measurement)
	Measured by electronic tensionmeter
Orthostatic hypotension detection	2 measures in standing position (first and then third minute)

	Comparison to the mean sitting measurement with each of the standing measurements	
	Measured by electronic tensionmeter	
	Impossibility to realize the test of orthostatic hypotension?	
	1. No 2. Yes	
	Orthostatic hypotension test positive?	
	1. No 2. Yes	
	3. Test non realizable	
	Orthostatic hypotension present if:	
	SBP differ≥20mmHg OR	
	DBP differ≥10mmHg	
Arterial stiffness evaluation	Pulse wave velocity	
	Measured by the mobilograph	
	Central Systolic Blood Pressure	
	Measured by the mobilograph	

3.1.5 Assessment subset 5: Balance and gait evaluation

This session consists of the evaluation of mainly three functions closely related to sarcopenia (10):

- Lower limb strength.
- Balance.
- Gait speed. More than other parameters, gait speed has shown a remarkable ability to predict survival in older adults and to reflect their general health and functional status (11).

Table 8 summarises this sub questionnaire.

Table 8. BALANCE AND GAIT EVALUATION

Lower limb strength	Raise from the chair 5 times without helping from the arms
	Number of seconds necessary to accomplish the task
	"Test non realizable" option will be provided
Balance	Single foot station
	1. <5sec
	2. >5sec)
	3. Test non realizable
Gait speed	Timed Get Up And Go Test
	Time in seconds needed to complete the task
	Speed for 4 meters' straight walk
	Time in seconds needed to complete the task
	Optional open text field will be provided in order to enter qualitative evaluation of the gait, the balance, the turn and the posture
Special conditions	Existence of a temporary condition that could affect the performance in these tests?
	1. No 2. Yes
	If yes, the evaluation should be repeated in another visit after the resolution of the condition.

During this part of the clinical assessment, movement monitoring data will also be obtained by IMUs (Inertial Measurement Units) which will be attached to the subject's upper and lower limbs since the beginning of the clinical assessment appointment. The aim of this action is to record some movement, posture and activity data from these devices during the 2 hours that lasts the appointment, also in a more standardized procedure that is the gait and balance evaluation tests. The gathering of these data will serve in the development of the WWBS (Wearable WBan System).

3.1.6 Assessment subset 6: Fried's criteria of frailty

This sub questionnaire (table 9) summarizes the criteria which are used to categorize the participants in three groups according to their level of frailty. Three out of five are based on questions done to the participants themselves, while the criterion of the gait speed is extrapolated from the previous subset "balance and gait evaluation" and the grip strength is measured with the electronic dynamometer. In the absence of any criterion the subject is characterized as non-frail, in the presence of 1-2 criteria as pre-frail and in the presence of three or more criteria as frail.

In the rare case of inadequate data to criteria identification due to lack of validity in the selfreported questions (if the person does not know or does not remember), the estimation of the physician will be employed in order to better categorize the subject, taking into account the overall findings of the whole clinical evaluation session.

1) Unintentional weight loss >4.5 kg in the	Question to the participant:
past year	"Have you unintentionally lost more than 4.5 kg in
	the past year?"
	1. No
	2. Yes
	3. I don't know
2) <20th population centile for grip strength	Dynamometer measured grip strength (average of
	3 trials, dominant hand)
	Normal values:
	[Men]
	>29kg for BMI≤24,
	>30kg for BMI 24.1-28 and
	>32kg for BMI >28
	[Women]
	>17kg for BMI≤23
	>17.3kg for BMI 23.1-26
	>18kg for BMI 26.1-29
	>21kg for BMI >29
	Result outside the norms? Yes/No
3) Self-reported exhaustion	Questions to the participant:
	 a) I felt that everything I did was an effort in the last week:

Table 9. FRIED'S CRITERIA OF FRAILTY

	 Rarely or none of the time (<1 day) Some or little of the time (1 to 2 days) Moderate amount of the time (3 to 4 days) Most of the time b) I could not get going in the last week Rarely or none of the time (<1 day) Some or little of the time (1 to 2 days) Moderate amount of the time (3 to 4 days) Moderate amount of the time (3 to 4 days) Most of the time
	Meets criteria for frailty if answer "moderate amount of the time" or "most of the time" for either question: yes/no
4) Low physical activity such that persons would only rarely undertake a short walk	Question to the participant: "Gait requiring physical activity during less than 10min per day (or 75min per week) in average"?
5) Slowed walking speed, defined as lowest population quartile on 4 minute walking test.	Extrapolated from previous walking test. Abnormal values for walking 4.57 meters: For men; ≥7seconds for height ≤173cm and ≥6seconds for height>173cm. For women; ≥7seconds for height ≤159cm and ≥6seconds for height>159cm. Is the gait speed slower? 1. No 2. Yes 3. Test not adequate (non realizable or acute debilitating condition that affects walking) In case of acute condition affecting standard gait speed the evaluation should be repeated in another visit after the resolution of the condition.
Categorization by Fried	 Non frail (0 criteria) Pre-frail (1-2 criteria) Frail (3 or more criteria)
The case of inadequate data	 Adequate data for the Fried's criteria 1. YES (if all the criteria above where answered by Yes or No) 2. NO (if we have missing data, ex gait speed non evaluable, weight loss not able to be reported etc)

Fried's categorization according to clinician's estimation: 1. Non frail 2. Pre-frail 3. Frail
Optional free text space will be provided in order to specify special cases of inadequate data

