Annex 19- Operational procedures' check lists

A. Clinical Evaluation Visit

The participant should be asked to bring:

- \checkmark A medication prescription or the boxes of the medication they take
- ✓ Samples of older written texts they produced
- ✓ Their glasses and/or their hearing aid
- ✓ Comfortable shoes
- ✓ Their walking aid if there is one

The investigator should make sure that the "clinical evaluation visit kit" contains:

- ✓ Papers/ questionnaires/ consent forms
- ✓ Pens
- ✓ Pencil (for the MMSE)
- ✓ Watch (for the MMSE)
- Measure tape (for body circumferences measurements and the definition of the 3 meter distances for the gait tests)
- ✓ Electronic scale
- ✓ Stopwatch (for gait tests)
- ✓ Electronic tensionmeter
- ✓ Mobilograph
- ✓ Tablet(with internet connection)+ charger
- ✓ Dynamometer + batteries
- ✓ Ruler (to quantify the VAS)
- ✓ IMUs

B. The FrailSafe session home visit

The nurse should make sure that for each visit the "FS home suitcase" contains:

- ✓ Her own smartphone
- ✓ The smartphone for the participant +charger
- ✓ Some phone cases in order the participant to choose which one suits him/her best
- ✓ The WWS device (straps): if should be cleaned +charger
- ✓ The tablet +charger
- ✓ The dynamometer
- ✓ The tensionmeter
- ✓ The beacons
- ✓ The AR glasses
- ✓ The plug adaptors needed for some devices (WWS electronic box, smartphones etc)
- ✓ The power strip for multiple plug charging

- ✓ Batteries
- ✓ Measure tape (in case some gait tests are required)
- ✓ Stopwatch (in case some gait tests are required)
- ✓ Paper/pen material in case of written text dictation
- ✓ Blood sampling material (only for the first visit)
- ✓ Any educational and informative material each center prepares to facilitate the education of the participants in the use of the FS system material
- The housing evaluation questionnaire and phone follow up questionnaires in paper form
- ✓ Disinfecting product to clean up the devices if needed

Note: in case of more than one FS home visits per day, this material should be multiplied accordingly

Tasks and actions in practice:

Before the visit

- ✓ Contact the participant and fix the appointment for the FS visit
- ✓ Verify that all required material are available and ready for use

During the installation visit

- ✓ Blood sample (only first visit)
- Explication of the use, the purposes and the technical issues of the FrailSafe material: educate the participants and check their comprehension
 - WWS:

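### Table 9 judges a walk timed over 4 m by cut-offs for 4.57 m with no stated conversion, and equates 10 min/day with 75 min/week, so Fried categories may be assigned inconsistently

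*Protocol*

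**What the plan says.** **Slowness**
- Protocol Section 3.1.5, Table 8, has one straight walk, "Speed for 4 meters' straight walk", with the result entered in seconds. The other gait test there is the Timed Get Up and Go.
- Section 3.1.6 says that "the criterion of the gait speed is extrapolated from the previous subset", and Table 9 repeats "Extrapolated from previous walking test". Neither place gives a formula.
- The same row of Table 9 gives its limits under "Abnormal values for walking 4.57 meters": for men, "≥7seconds for height ≤173cm and ≥6seconds for height>173cm". For women the limits are also 7 s and 6 s, split at 159 cm.
- The row describes slowness as "lowest population quartile on 4 minute walking test".
- The Annex 19 kit list includes a tape for "definition of the 3 meter distances for the gait tests".

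**Activity**
- Table 9 asks about "Gait requiring physical activity during less than 10min per day (or 75min per week) in average".

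**Use of the categories**
- No criterion means non-frail, one or two pre-frail, three or more frail.
- Section 2.4 sets a 1.5:1.5:1 ratio over groups A and B combined, and a minimum of 7 people per lead-comorbidity cell within each frailty category.
- Section 3.6.1 takes 20 people per category into the autonomic substudy, which runs in Patras only.
- Section 2.4 also says that the Fried strata play no part in the data analysis.

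**The concern.** The assessor has a time in seconds over 4 m, a limit in seconds for 4.57 m, and a yes/no box. Two people following the protocol faithfully can fill that box differently: one rescales the time to 4.57 m, the other compares it as it stands. The activity item has the same defect on a smaller scale, because its two limits are not the same amount of walking.

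Each criterion counts one point. An error therefore changes the category of someone whose other criteria put them at the 0/1 boundary (non-frail or pre-frail) or the 2/3 boundary (pre-frail or frail). At stake are the recruitment mix in A and B, the comorbidity minimums, and above all the autonomic substudy, where the category is the exposure being studied.

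**Working it through.** **Activity.** The protocol's weekly figure is 75 min. From its own daily figure, 10 min × 7 days = 70 min, so 75 does not reproduce. The reverse, 75 / 7, is 10.71 min/day. A person averaging 70 to under 75 min/week is below the weekly limit but not below the daily one.

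**Slowness.** Inputs: cut-offs 7 s and 6 s over 4.57 m (Table 9); timed distance 4 m (Table 8). Constant speed is assumed over this short walk.

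| Quantity | Formula | 7 s | 6 s |
|---|---|---|---|
| Speed implied by Table 9 | 4.57 / t | 0.653 m/s | 0.762 m/s |
| Equivalent time over 4 m | t × 4 / 4.57 | 6.13 s | 5.25 s |
| Speed limit if t is read off the 4 m time | 4 / t | 0.571 m/s | 0.667 m/s |
| Relative change in limit | 4 / 4.57 − 1 | −12.5% | −12.5% |

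Under the unscaled reading, people who take 6.13 to under 7 s (7 s stratum) or 5.25 to under 6 s (6 s stratum) over 4 m are recorded as not slow. The error runs one way only. If the 4 m time is multiplied by 4.57 / 4 = 1.1425 before comparison, there is no error.

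**Share affected if unscaled.** The protocol gives no gait-speed distribution. As an illustration only, assume a normal distribution with mean m and SD s. The affected share is Φ((4.57/t − m)/s) − Φ((4/t − m)/s):

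| Mean, SD (m/s) | 7 s stratum | 6 s stratum |
|---|---|---|
| 0.8, 0.20 | 0.231 − 0.127 = 0.104 | 0.424 − 0.252 = 0.172 |
| 0.8, 0.25 | 0.278 − 0.180 = 0.098 | 0.439 − 0.297 = 0.142 |
| 0.9, 0.20 | 0.108 − 0.050 = 0.058 | 0.245 − 0.122 = 0.123 |
| 1.0, 0.25 | 0.082 − 0.043 = 0.039 | 0.170 − 0.091 = 0.079 |
| 1.1, 0.20 | 0.013 − 0.004 = 0.009 | 0.045 − 0.015 = 0.030 |

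This is about 1–10% of participants in the 7 s stratum and 3–17% in the 6 s stratum. Fewer would change category, because only those at the 0/1 or 2/3 boundary do.

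**What the ratio implies.** A and B hold 3 × (80 + 40) = 360 people, so 1.5:1.5:1 means 135, 135 and 90.

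**The case against.** The strongest reply is that Section 3.1.6 and Table 9 both say the criterion is extrapolated from the 4 m walk. That can mean rescaling by speed, and Table 9 does go on to ask about gait speed. On that reading the slowness criterion is correct. This stands: a reader might infer that the 4.57 m limits are applied raw and that categories are wrong, but the protocol does not say so. It is equally silent on the rescaling, and in Section 3.1.6 the word may mean no more than that the value is carried over from the earlier subset.

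A reader might also work out that a third to a half of slow walkers are missed. With mean 0.8–1.0 and SD 0.25 m/s the figure is 32–48% (for example 1 − 0.297/0.439 and 1 − 0.043/0.082). That needs both the unscaled reading and an assumed distribution, and it is a share of slow walkers, not of participants. The slow end of the range also fits poorly with a criterion described as a lowest quartile, since 44% would then be slow in the 6 s stratum.

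Other limits stand too. The 4-minute label looks like a slip for 4 metres, because results are in seconds. The 3 m in Annex 19 may belong to the Timed Get Up and Go, so it does not show that the straight walk was marked at 3 m. The activity gap is 5 minutes a week on a self-reported question. Section 2.4 promises the same criteria at all centres, and nothing shows that centres have diverged. That promise does not settle the matter, though, because the criteria it points to are themselves ambiguous.

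**Conclusion.** The point holds as an inconsistency in two classification thresholds. The 70 versus 75 min/week mismatch needs no assumption. The slowness mismatch is certain as text: two distances, no conversion and a wrong label. Its effect is conditional: none if centres rescale, and a 12.5% lower speed limit, always towards less frailty, if they do not. Categories may be misassigned, and differently between centres; the documents do not show that they are.

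A reader might infer that the main results are affected. They are not, through this route: Section 2.4 keeps the Fried strata out of the analysis, and the Clinical Frailty Index (Appendix I, Table 22) lists 4 m gait speed without reference to the 7 s and 6 s limits. Table 22 also lists low physical activity, but does not say that it uses the Table 9 threshold. The consequence is confined to the A and B ratio, the comorbidity minimums and the autonomic substudy, of which the last matters most.

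**What to change.** - Reconcile Tables 8 and 9: state the distance walked, and give the slowness limits as speeds or as times for that distance. If the investigators keep the present 4.57 m limits, the equivalents are 0.653 and 0.762 m/s, or 6.13 s and 5.25 s over 4 m.
- Correct the 4-minute label, and make the Annex 19 distances agree with the tests they serve.
- State one activity threshold in one unit, chosen by the investigators.
- Ask each centre which distance was walked and how the time was compared. Then re-derive slowness from the recorded 4 m times and heights, at least for the autonomic substudy groups, and before C and D are recruited. Section 2.4 lets the comorbidity minimums be met in any group, so a shortfall found now could still be made up.

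The cost is wording plus a recalculation from data already held. The activity answer was recorded as yes or no, so it can only be clarified going forward. The downside is that category counts already reached in A and B may shift, and replacement in those groups ended at M19.
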